### 3.2 Adherence and protocol deviations

Reported in the 4-month assessment and the process evaluation.

In the 12-month evaluation, we will report on the number of control participants who accessed the SWiM website (1 session, 4 sessions, 8 sessions, 12 sessions) after being provided access after the 4-month assessment.

### 3.3 Analysis population

Individuals will be included in the analysis in the group to which they were randomised, regardless of the extent to which they adhered to the intervention. Participants with missing outcome data at follow-up will be excluded. Two per-protocol analyses will be conducted (see section 5.2).

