8. STATISTICS AND QUANTITATIVE DATA ANALYSIS

8.1 Statistical analysis

A detailed statistical analysis plan will be developed and signed off by the Trial Steering Committee (TSC) prior to analysis. Participants will be analysed in the group to which they were randomised, based on the intention-to-treat principle. The primary analysis will estimate the baseline-adjusted difference between intervention groups in change in weight from baseline to 4 months, using a linear regression model including randomisation group, baseline weight, and the randomisation stratifiers (sex, BMI classification). Participants with missing values of weight at 4 months will be excluded (ie, a complete-case analysis which assumes outcome data are missing at random conditional on covariates in the model). If there are >5% of participants with missing values of weight, a sensitivity analysis will be performed using multiple imputation by chained equations – this makes the missing at random assumption but provides increased precision compared with a complete-case analysis. Linear regression will be used to estimate the baseline-adjusted difference between intervention groups in change in weight from baseline to 12 months and 4 months to 12 months. Since the control group was waitlisted and therefore received access to the SWiM website after the 4-month follow-up, analyses at 12 months will need to account for intervention usage in the control group. Regression models for the 12-month follow-up will therefore include intervention engagement (as measured using the intervention engagement questionnaire and/or website analytics) as a covariate. Full details of this analysis will be provided in the statistical analysis plan. Continuous secondary outcomes will be analysed using the same method.

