### **Primary outcome**

The mean and SD of weight at baseline, 4-month and 12-month follow-up will be presented, together with the mean and SD of weight change from baseline to 4 months, 4 months to 12 months, and baseline to 12 months, separately in each randomised group.

The intervention effect on weight at 12 months (and 95% CI) will be estimated from a random intercepts linear regression model, using measures of change in weight at 4 months and 12 months as outcomes. The model will include intervention group, assessment timepoint, intervention by assessment timepoint interaction, the randomisation stratifiers (sex, BMI classification), and baseline value of weight as fixed effects, and random intercepts to allow for the repeated measures on each individual:

(Change in weight from baseline to timepoint t)i =  $\beta_0 + u_i + \beta_1 x$  groupi +  $\beta_2 x$  (t=4)i +  $\beta_{12} x$  (t=4)i\*groupi +  $\beta_3 x$  baselineweighti + randomisation stratifiers +  $\varepsilon_{it}$ 

*i*=individual, t=4 or 12 months (follow-up timepoint). (*t=4*)*i* = 1 if timepoint=4 months, 0 otherwise. *u**i* has a normal distribution with mean 0, variance  $\sigma_u^2$  and represents the (level 2) between-individual error. *ɛ**i*t has a normal distribution with mean 0, variance  $\sigma^2$  and represents the overall (level 1) residual error.

Then  $B_1$  represents the baseline-adjusted difference in weight change at 12 months comparing intervention vs control.

NOTE:  $\mathbf{6}_1 + \mathbf{6}_{12}$  represents the baseline-adjusted difference in weight change at 4 months comparing intervention vs control – not of interest in this analysis since it has previously been reported.

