### **Missing data**

We will conduct analyses with all observed data; random intercept models use all available data and assume missing data are missing at random. To explore this assumption, we will descriptively compare participants with and without missing outcome data on baseline characteristics.

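### SAP 3.3's exclusion of participants with missing follow-up outcomes is not reconciled with the all-observed-data model in SAP 5.2, and no missing-data sensitivity analysis remains

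*SAP*

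**What the plan says.** SAP 3.3 (Analysis population) keeps participants in their randomised group and then adds: "Participants with missing outcome data at follow-up will be excluded". It does not name the visit, nor say whether one missing visit is enough for exclusion.

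SAP 5.2 (Primary outcome) specifies a random-intercepts model "using measures of change in weight at 4 months and 12 months as outcomes". SAP 5.2 (Missing data) adds: "We will conduct analyses with all observed data; random intercept models use all available data and assume missing data are missing at random". The only follow-up to that assumption is this: "To explore this assumption, we will descriptively compare participants with and without missing outcome data on baseline characteristics".

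Protocol 8.1 planned a complete-case regression at 4 months. If more than 5% of weights were missing, "a sensitivity analysis will be performed using multiple imputation by chained equations". The SAP's analysis text plans no imputation. SAP 5.5, which lists departures from the protocol, mentions only the move from linear regression to the random-intercepts model.

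**The concern.** Someone with a 4-month weight but no 12-month weight stays in the model under SAP 5.2 and leaves it under the plain reading of 3.3. That reading is the natural one, because SAP 3.1 and 5.1 define the primary outcome as change to 12 months, and SAP 4.4 counts loss as not completing the 12-month measures. Two analysts could each follow the SAP and report different primary estimates.

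The choice matters if people who had gained weight by 4 months were less likely to return at 12 months, and more so in one arm than in the other. Weight is self-reported online (Protocol 7.2), participants know their allocation (Protocol 15), and the arms had different experiences, so this is plausible. It is not shown. A separate risk is loss that depends on the 12-month weight itself. Neither analysis set deals with that, and the SAP plans nothing to gauge it.

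**Working it through.** **1. The plan's own figure.** Protocol 8.2 gives a 1 kg difference at 4 months, SD 6 kg, correlation 0.9, 90% power, 5% significance (taken as two-sided) and 20% drop-out.

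- Baseline-adjusted SD = 6 × √(1 − 0.9²) = 2.615 kg.
- n per arm = 2 × (1.960 + 1.282)² × 2.615² / 1² = 143.7, so 144.
- 144 / 0.80 = 180 per arm, 360 in total.

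This matches the protocol, so there is no sample-size error here. The 1 kg serves below only as a yardstick; the documents give no 12-month design difference.

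**2. The two readings of 3.3.** If it means no follow-up weight at all, it agrees with 5.2, since such a person contributes no outcome to the model. If it means any follow-up weight missing, the 4-month weights of 12-month drop-outs are discarded.

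**3. Size under the second reading.** The SAP model was simulated with 192 and 196 participants (SAP 2.5), SD 6 kg, 1,500 replicates per scenario and a Monte Carlo error of about 0.01 kg. Assumptions not in the documents: correlation 0.9 also holds at 12 months; everyone is seen at 4 months; nominal 12-month loss is 20% or 35%; the log-odds of loss change by 0.2 or 0.4 per kg. Unless stated, the true effect is zero. Estimates are SWiM minus control, in kg; each range runs from slope 0.2 to slope 0.4.

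| Loss mechanism | All observed data | Exclusion, 20% loss | Exclusion, 35% loss |
|---|---|---|---|
| Completely at random | about 0 | about 0 | about 0 |
| On 4-month change, same in both arms | about 0 | about 0 | about 0 |
| On 4-month change, control only | about 0 | 0.13 to 0.26 | 0.23 to 0.40 |
| On 4-month change, opposite in the arms | about 0 | 0.27 to 0.52 | 0.45 to 0.81 |
| On unseen 12-month change, control only | 0.22 to 0.43 (20%); 0.36 to 0.65 (35%) | 0.28 to 0.56 | 0.46 to 0.83 |

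Under loss completely at random, exclusion raises the standard error from 0.291 to 0.298 kg (0.298 / 0.291 = 1.02) at 20% loss, and from 0.316 to 0.330 kg (0.330 / 0.316 = 1.04) at 35%. With equal dependence and a true 1 kg effect, exclusion estimates 0.93 to 0.99 kg.

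**4. Does using all observed data remove the bias?** That depends on the 12-month SD and correlation. The inputs in step 3 imply equal residual SDs at both visits and a residual correlation of (0.9 − 0.81) / (1 − 0.81) = 0.47. This fits the random-intercepts structure, and the bias vanishes.

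Now assume instead residual SDs of 2.62 kg (4 months) and 3.6 kg (12 months), correlation 0.65 and about 25% loss:

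| Slope per kg, SWiM vs control | Exclusion | SAP model, all data |
|---|---|---|
| 0.4 vs 0.1 | −0.37 to −0.42 | −0.13 to −0.15 |
| 0.5 vs 0 | −0.61 to −0.70 | −0.21 to −0.28 |
| Equal | about 0 | about 0 |

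The ranges cover runs that set the loss rate slightly differently. The remainder arises because the model assumes one variance for both visits. The true slope of the 12-month on the 4-month residual is 0.65 × 3.6 / 2.62 = 0.89. The model implies about 0.65 × 2.62 × 3.6 / [(2.62² + 3.6²) / 2] = 0.62, so it under-corrects. An unstructured covariance gave +0.01 and −0.01 kg for the two unequal cases.

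The same slopes with step 3's SD and correlation give exclusion bias of about −0.2 and −0.3 kg, and about 0 with all data.

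**5. The planned check.** To explore the assumption, "we will descriptively compare participants with and without missing outcome data on baseline characteristics". This can show that loss is related to baseline factors. It cannot separate loss at random from loss that depends on the missing weight, and it leaves out 4-month weight change by arm, which is observed and more informative.

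**The case against.** The strongest defence is that 3.3 is loosely worded rather than wrong. SAP 5.2 is the specific analysis instruction and plainly says all observed data; 3.3 can be read to agree with it. A reader might infer that the two sections cannot both be followed. The text does not support that, because 3.3 leaves open which visit and how many. The ambiguity stands, since nothing in 3.3 states the harmless reading.

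A reader might also infer that exclusion defeats SAP 5.5's reason for choosing the mixed model. It does not: 5.5 cites repeated measures on each individual, and completers still have those. What is lost is the property claimed in 5.2, that "random intercept models use all available data and assume missing data are missing at random".

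On the check, the SAP says only that it will explore the assumption, and no descriptive comparison can detect dependence on unseen values. SAP 4.4 also reports loss, exclusions and withdrawals by arm, the last two with reasons. That is fair, and it leaves the lack of any sensitivity analysis as the substantive gap.

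On imputation, the protocol offered it under missing at random, for precision relative to complete cases. A likelihood model on all follow-up weights makes the same assumption, so imputation of that kind would largely duplicate it. Its removal is therefore mainly a matter of declaration. The gap it leaves matters for departures from missing at random.

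**Conclusion.** The point holds as an unreconciled analysis-set rule together with a missing sensitivity analysis. It should be fixed before the 12-month analysis.

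A reader might infer that the primary result will be biased. The documents do not support this: they give neither a 12-month loss rate nor a mechanism. Exclusion costs 2 to 4% in standard error under loss completely at random, and causes almost no bias when dependence on 4-month change is equal in both arms. Bias of roughly 0.1 to 0.8 kg, in either direction, needs dependence that differs by arm and rests on assumed loss of 20 to 35% and slopes up to 0.5 per kg. The upper end requires strong, opposite mechanisms in the two arms.

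Following 5.2 removes all or most of that bias, depending on the 12-month SD and correlation. It does not cure loss driven by the unseen 12-month weight, where both approaches were biased (0.22 to 0.65 kg with all data, 0.28 to 0.83 kg with exclusion, under the assumptions shown).

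**What to change.** 1. Replace the exclusion sentence in SAP 3.3 with: *For each outcome, all randomised participants with that outcome recorded at 4 or 12 months are included in the repeated-measures model in their randomised group; only those with neither are excluded. The 4-to-12-month change model uses participants with both weights.* This covers the secondary outcomes, and also the regression in 5.2 that cannot run without both weights.
2. Extend the descriptive comparison of those with and without 12-month data to include 4-month weight change, by arm.
3. Add one multiple-imputation sensitivity analysis for 12-month weight, imputing separately by arm and using 4-month weight. Shift the imputed values by arm-specific amounts over a range that the team states in advance, and report where the conclusion changes. A zero shift restores the protocol's imputation under missing at random.
4. Record in SAP 5.5 how the protocol's imputation analysis has been changed.

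The cost is a few lines of SAP text and one extra sensitivity analysis. No new data are needed.

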# 4 Trial population

### 4.1 Screening data

Participants completed an online screening questionnaire which assessed:

- Age
- Weight, height (to assess BMI)
- Good understanding of written English (yes/no)
- Bariatric surgery (yes/no)
- Whether they own a set of scales

### 4.2 Eligibility criteria

See section 4 in the study protocol.

### 4.3 Recruitment

We will report:

- Number of participants assessed for eligibility
- Number of participants randomised to each study arm
- Number of participants who completed baseline measures
- Number of participants who completed 4-month follow-up
- Number of participants who completed 12-month follow-up
- Number of participants included in the main analysis (record reasons for any exclusions) and in the 2 per-protocol analyses.

### 4.4 Withdrawal/loss to follow-up

Withdrawal/loss to follow-up will be presented by randomised group, specifically:

- Number of participants who do not complete measures at 12-month follow-up
- Number of participants excluded from the analyses (with reasons)
- Number of participants who withdraw (with reasons)

### 4.5 Baseline characteristics

The following baseline characteristics of the study sample will be summarised separately within each randomised group and for the total sample:

- Age (years) (range, mean, SD)
- Sex (female/male/other)
- Ethnicity
- Educational qualifications
- Occupational status
- Marital status
- Body-mass-index (kg/m^2)
- Proportion of participants reporting BMI in the following categories: 25-<30, 30-<40, 40+

For continuous variables, means and standard deviations (SDs) will be presented, unless the variable has a skewed distribution, in which case medians, 25th and 75th percentiles will be presented. For categorical variables, the number and percentage of individuals within each category will be presented. For each variable (continuous or categorical), the percentage of missing values will be calculated. For the categorical variables, percentages within subcategories will be calculated using the number of non-missing values as the denominator.

P-values for comparing the two study groups on baseline characteristics will not be reported as per the CONSORT statement (4).

### 5 Analysis

### 5.1 Outcome definitions

### **Primary Outcome**

Change in self-reported weight from baseline to 12-month follow-up (kg).

### **Secondary Outcomes**

All secondary outcomes will be defined as change in outcomes (Table 2) from baseline to 12 month follow-up.

Outcome	Type of outcome	Measure
Depression (depressive	Continuous, summary	Patient Health Questionnaire
symptom severity)	score	8-item (PHQ-8)
Anxiety (anxious symptom	Continuous, summary	Generalized Anxiety Disorder
severity)	score	7-item (GAD-7) scale
 		
Perceived stress	Continuous, summary	Perceived Stress Scale (PSS-4)
Baychological flowibility	Continuous summary	Accontance and Action
	continuous, summary	Acceptance and Action
	score	
		(Revised) (AAQVV-R)
Eating behaviour:	Continuous, summary	Three-Factor Eating

 
cognitive restraint
 
	score for each subscale	Questionnaire (TFEQ-R21)

 
uncontrolled eating
 
		

 
emotional eating
 
		
Volume of total physical	Continuous, MET-min	International Physical Activity
activity	per week	Questionnaire (IPAQ)
Health related quality of life	Continuous, summary	EQ-5D-L
	score	
Wellbeing/capability	Continuous, summary	ICECAP-A
	score	

(For details and references, see section 6 in the study protocol)

### 5.2 Analysis methods

### Descriptive analyses

See section 4.5 "Baseline characteristics".

### **Primary outcome**

The mean and SD of weight at baseline, 4-month and 12-month follow-up will be presented, together with the mean and SD of weight change from baseline to 4 months, 4 months to 12 months, and baseline to 12 months, separately in each randomised group.

The intervention effect on weight at 12 months (and 95% CI) will be estimated from a random intercepts linear regression model, using measures of change in weight at 4 months and 12 months as outcomes. The model will include intervention group, assessment timepoint, intervention by assessment timepoint interaction, the randomisation stratifiers (sex, BMI classification), and baseline value of weight as fixed effects, and random intercepts to allow for the repeated measures on each individual:

(Change in weight from baseline to timepoint t)i =  $\beta_0 + u_i + \beta_1 x$  groupi +  $\beta_2 x$  (t=4)i +  $\beta_{12} x$  (t=4)i\*groupi +  $\beta_3 x$  baselineweighti + randomisation stratifiers +  $\varepsilon_{it}$ 

*i*=individual, t=4 or 12 months (follow-up timepoint). (*t=4*)*i* = 1 if timepoint=4 months, 0 otherwise. *u**i* has a normal distribution with mean 0, variance  $\sigma_u^2$  and represents the (level 2) between-individual error. *ɛ**i*t has a normal distribution with mean 0, variance  $\sigma^2$  and represents the overall (level 1) residual error.

Then  $B_1$  represents the baseline-adjusted difference in weight change at 12 months comparing intervention vs control.

NOTE:  $\mathbf{6}_1 + \mathbf{6}_{12}$  represents the baseline-adjusted difference in weight change at 4 months comparing intervention vs control – not of interest in this analysis since it has previously been reported.

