### Secondary outcomes

Continuous secondary outcomes will be analysed using the same approach as described for the primary outcome.

We will estimate baseline-adjusted differences between the study groups in change in weight from 4 months to 12 months using a linear regression model with change in weight from 4 months to 12 months as the outcome, and including baseline weight, 4 month weight, the randomisation stratifiers (sex, BMI classification) and intervention group as covariates.

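### The primary random-intercepts model assumes weight change is equally variable at 4 and 12 months; if it is not, the confirmatory 12-month interval is miscalibrated

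*SAP*

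**What the plan says.** SAP 3.1 names weight change from baseline to 12 months as the single confirmatory endpoint and limits p-values to the primary outcome. SAP 5.2 (Primary outcome) says: "The intervention effect on weight at 12 months (and 95% CI) will be estimated from a random intercepts linear regression model", with the changes at 4 and 12 months as joint outcomes. On the fixed effects it says: "The model will include intervention group, assessment timepoint, intervention by assessment timepoint interaction, the randomisation stratifiers (sex, BMI classification), and baseline value of weight". The coefficient of group, beta1, is the 12-month effect.

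Two random terms follow. The intercept u_i "represents the (level 2) between-individual error" and has variance sigma_u^2. The term epsilon_it "represents the overall (level 1) residual error" and has variance sigma^2. Neither variance depends on the visit.

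Under Testing assumptions, heteroscedasticity is examined by plotting standardised residuals against predicted values, and no action is named if the plot looks poor. The remark there about large samples concerns normality only. SAP 5.2 also has the SDs of weight change reported for each interval and arm, and extends the primary approach to the continuous secondary outcomes.

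On who is analysed, SAP 3.3 says: "Participants with missing outcome data at follow-up will be excluded". SAP 5.2 (Missing data) says instead that all observed data are used and that "random intercept models use all available data and assume missing data are missing at random".

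**The concern.** With one sigma_u^2 and one sigma^2, the modelled variance of weight change is sigma_u^2 + sigma^2 at both visits. If the true variances differ, the pooled value is wrong for each visit, and the 95% interval and p-value for beta1 do not have their stated properties. This is the trial's one confirmatory result at 12 months.

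Nothing in the plan would correct it. The residual plot is not split by visit. The reported SDs would show a discrepancy without altering the model. No robust standard error or visit-specific variance is named. Protocol 8.1 planned a linear regression of the 12-month change, which estimates its own residual variance. SAP 5.5 justifies the move to random intercepts by the repeated measures and does not discuss variance.

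There is a smaller, linked matter. A participant with a 4-month weight but no 12-month weight is included under SAP 5.2 and arguably excluded under 3.3, so the analysed number is ambiguous.

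**Working it through.** **Inputs from the documents.** Protocol 8.2: SD of weight 6 kg, correlation between repeated measures 0.9, difference 1 kg at 4 months, 90% power, 5% level, 20% dropout, N = 360. SAP 2.5: 192 and 196 randomised.

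**Assumed, because the documents give no figure.** The baseline-to-12-month correlation r12; in the simulation also the 4-to-12-month correlation (0.8 to 0.92) and missingness of 15% at 4 months and 25% at 12 months.

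**Reproducing the plan's figure.** Baseline-adjusted residual variance at 4 months: v4 = 36 x (1 - 0.9^2) = 6.84, SD 2.615 kg. Per arm, with a two-sided test: 2 x (1.960 + 1.282)^2 x 6.84 / 1^2 = 143.8, so 144. Then 144 / 0.8 = 180 per arm, 360 in total. This matches the protocol exactly, so 2.615 kg is the 4-month residual SD behind the design.

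**Standard error under the SAP model.** With complete data and a group-by-time term, the estimate of beta1 is essentially the 12-month group difference. Its model-based variance is (sigma_u^2 + sigma^2)(1/n1 + 1/n0), and the fit sets sigma_u^2 + sigma^2 to about (v4 + v12)/2. The true variance uses v12. Hence

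- SE ratio (model / true) = sqrt[ ((v4 + v12)/2) / v12 ]
- actual type I error = 2 x (1 - Phi(1.96 x ratio))

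with v12 = 36 x (1 - r12^2) and v4 fixed at 6.84:

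| r12 (assumed) | v12 | SD at 12 months (kg) | average variance | SE ratio | type I error |
|---|---|---|---|---|---|
| 0.95 | 3.51 | 1.87 | 5.175 | 1.214 | 1.7% |
| 0.90 | 6.84 | 2.62 | 6.84 | 1.000 | 5.0% |
| 0.85 | 9.99 | 3.16 | 8.415 | 0.918 | 7.2% |
| 0.80 | 12.96 | 3.60 | 9.90 | 0.874 | 8.7% |
| 0.70 | 18.36 | 4.28 | 12.60 | 0.828 | 10.4% |

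In kilograms, at r12 = 0.80 with all 388 followed up: sqrt(1/192 + 1/196) = 0.1015. The model SE is sqrt(9.90) x 0.1015 = 0.32 and the true SE is 3.60 x 0.1015 = 0.37.

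**Bound.** As v12 grows, the ratio tends to sqrt(1/2) = 0.71. With similar numbers at both visits the understatement therefore cannot exceed about 29%, with type I error of about 17%.

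**Simulation.** REML fit of the SAP's model (stratifiers omitted), 192/196 participants, no true effect, 2,000 runs per setting:

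| r12 | complete data: SE ratio, type I error | 15%/25% missing: SE ratio, type I error |
|---|---|---|
| 0.95 | 1.18, 2.5% | 1.25, 1.5% |
| 0.90 | 0.99, 5.6% | 1.02, 4.0% |
| 0.85 | 0.91, 7.2% | 0.91, 7.9% |
| 0.80 | 0.89, 8.1% | 0.85, 9.7% |
| 0.70 | 0.82, 10.9% | 0.82, 11.4% |

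The formula and the simulation agree closely. In the same runs, an analysis of covariance at 12 months alone, with its own residual variance, kept type I error between 4.2% and 5.9%.

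**The case against.** The strongest objection is that nothing in the documents shows unequal variances. The only variability figures are those in Protocol 8.2, and if its correlation of 0.9 also holds at 12 months, the model is correctly calibrated. That stands. A reader might infer that the 12-month standard error is certainly too small; the documents do not support this, since equal variances give no error and a smaller 12-month variance makes the interval too wide. A reader might also infer that precision is taken from the 4-month data alone. It comes from about the average of the two variances, which limits the damage, and with complete data the point estimate is essentially unaffected.

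Two neighbouring criticisms are also weaker than they look. The separate regression for change from 4 to 12 months, "including baseline weight, 4 month weight, the randomisation stratifiers (sex, BMI classification) and intervention group as covariates", conditions on a post-randomisation weight. It therefore answers a different question from the contrast -beta12 in the primary model. Calling the difference a bias presumes that the unconditional contrast is the target. The analysis is secondary and carries no p-value, and SAP 1.1 reports 4-month data consistent with no effect on bodyweight. It need not be dropped.

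Similarly, SAP 3.3 does not say which follow-up must be missing. Read as no follow-up weight at all, it agrees with 5.2, so loss of the missing-at-random protection follows only under the stricter reading.

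The objection does not supply a reason to keep the constraint. The interval is correctly calibrated only if the two variances happen to match, and the plan has no step that responds if they do not.

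**Conclusion.** The point holds as a conditional one. Equal variance at 4 and 12 months is a certain feature of the model as written; the direction and size of the resulting error are not known from the documents. Greater spread at 12 months is plausible, because follow-up is three times as long and controls can take up SWiM to varying degrees between the visits (SAP 2.2 and 3.2).

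The estimated understatement of 8% to 17% rests on r12 between 0.85 and 0.70, on a weight SD of 6 kg at every visit, and on the protocol's 4-month correlation. The table also shows the null and the conservative cases. The change is worth making before the 12-month analysis because it is nearly free and corrects miscalibration whichever way it runs. The mismatch between SAP 3.3 and 5.2 is a minor wording point to settle at the same time.

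**What to change.** In SAP 5.2, keep the fixed effects and replace the random intercept by an unstructured 2x2 residual covariance: a separate variance at each visit plus a covariance, with Kenward-Roger or Satterthwaite degrees of freedom. Use the same model for the continuous secondary outcomes that follow the primary approach.

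In SAP 3.3, state that all randomised participants with at least one follow-up weight are included in the primary analysis, so that it agrees with the Missing data paragraph.

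The cost is a few lines of SAP text and one changed model call in R or Stata, the packages named in SAP 5.4. There are three covariance parameters instead of two, and the 12-month interval may be slightly wider. If the team prefers to keep the random intercept, robust standard errors or a 12-month analysis of covariance as a sensitivity analysis would address the same weakness less directly.
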